We will recruit from universities and schools as they employ a range of people from cleaners and domestic staff to teachers and lecturers, and a variety of ages. This will provide a variety of women from whom to sample. Youth centres will be particularly helpful in recruiting young women who may not wish to accept an invitation through their place of education.

Research Process

The interview schedule will be developed in the UK and then translated to ensure consistency of data collection. Interviews will be conducted either face-to-face, by telephone or skype according to the respondents' preference. Interviews will last 30 minutes and will be audio-recorded. They will be conducted in people's native language. Participants will be encouraged to discuss the issues raised in their own terms, with prompts from the researcher. Their sources of knowledge will be explored (with prompts including the influence of factors such as information from medical professionals, information from the internet and written information included in packs). They will also be asked about any recent changes in information and advice about CHCs. Interviews will also explore women's awareness of regulators as a source of information about CHCs. This will include consideration of if, and if so how, they became aware of advice from regulators concerning CHCs, how they perceived this information and the way in which it was communicated. The interviews will focus in particular on suggestions for improvement in communication from regulators. All women will receive a 20 euro voucher by way of thanks for their participation.

Analysis

Interviews will be conducted in people's native language, and then transcribed and translated in to English so all the analysis can be conducted by one site (UK) to ensure comparability of approach and rigour. Framework analysis will be employed to aid comparability across the sites. Once the interviews are transcribed, they will be read repeatedly and key themes will be identified and noted to produce a detailed understanding of how information about the risks of CHCs, specifically the risks of thromboembolism, is presented, where it appears and in what context. We will also consider women's suggestions for optimal communication about the risks of VTE associated with taking CHC. The data generated will be discussed with both the steering and advisory group.

WP4

Aim of WP

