Semi-structured interviews will be conducted with up to 24 health professionals to explore (i) knowledge, (ii) attitudes and (ii) prescribing practices in relation to CHCs; with a specific focus on the risks of VTE.

Sample

Up to 24 health professionals involved in the prescription of CHC will be recruited. The place of recruitment will vary according to country. Qualitative interview studies usually aim for between 20 and 30 participants to ensure saturation of themes from the data. We will aim for 8 participants from each of the three target countries, with a lower limit of 6 and a higher limit of 10 in each country. Data will be collected in each country until we feel we have saturation however we believe this sample size will allow us to successfully sample a range of characteristics (specifically; age, type of practitioner (nurse, doctor), location of practice (rural, urban) in each country.

Research Process

Interviews will be conducted either face-to-face, by telephone or skype according to the respondents' preference. Interviews will last 30 minutes and will be audio-recorded. They will be conducted in the respondents' native language. Participants will be encouraged to discuss the issues raised in their own terms, with prompts from the researcher. Interviews will explore the sources of information health professionals utilise when advising women; likely prompts include colleagues, training, information provided in updates and continuing professional development. Practitioners will be asked specifically about their familiarity with information from regulators such as the EMA. They will also be asked specifically about updates to information, their awareness of updates, if they proactively seek them and how they fit into their clinical practice.

We are particularly interested in perceptions of advice about CHCs from regulators, for example if, and if so how, they have received advice from the regulators concerning CHCs and how they perceived this information and the manner of communication. After providing their views we will show them the advice provided following the review by the EMA and ask them how familiar they are with it. Ideas for improvement in communication from the regulator will be proactively sought. We will also explore the extent to which health professionals report using information from updates

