in practice, particular in relation to renewing an existing prescription for CHCs; which provides the opportunity to reassess the suitability of the CHC for the woman concerned. All health practitioners will receive a 20 euro voucher by way of thanks for their participation.

Analysis

Interviews will be conducted in respondents' native language, transcribed and translated in to English so all the analysis can be conducted by one site (UK) to ensure comparability of approach and rigour. Framework analysis will be employed to aid comparability of data from different countries. Once the interviews are transcribed, they will be read repeatedly and key themes will be identified and noted to produce a detailed understanding of how information about the risks of CHCs, specifically the risks of thromboembolism, is discussed and in what context. We will also consider suggestions for optimal communication about the risks of VTE associated with taking CHC. The data generated will be discussed with the steering and advisory group.

WP5

Aim of WP

The findings from WP1-4 will be used to develop a survey in electronic format for women of childbearing age (16-49 years), to explore: (i) if they sought information when making decisions about CHC, and if so from where, (ii) perceptions of risk in response to short scenarios based on previously collected interview data, (iii) awareness of information from the EMA, (iv) what optimal communication from regulators would look like.

Sample

The survey will be distributed via local organisations such as schools, colleges and youth centres in up to six European Union Member States (Denmark, Germany, UK, Slovakia, The Netherlands and Spain). Educational institutions employ a range of people from cleaners and domestic staff to teachers and lecturers, and a variety of ages. This will provide a range of women from whom to sample. Youth centres will be particularly helpful in recruiting young women who may not wish to accept an invitation through their place of education.

Eligibility will be assessed via an initial filter page that will check potential participants are between the ages of 16 and 49 years. We will seek responses from 100 women in each country; with an aim to recruit 10% who have chosen to use an alternative to CHC.

Research process

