Surveys presented online generally get a reasonable response rate as people can answer questions at a time that is convenient to them, in privacy and with minimal effort, a key aspect being they don't need to speak to a researcher or receive or return an item by post. This also makes them cost-effective. Recruitment will be done via links with local organisations such as schools, colleges and youth centres. We will aim to recruit up to 600 women (100 per country), with an aim to recruit 10% in each country who have chosen to use an alternative to CHC. The recruitment information will differ to recruit women taking and not taking CHC. If women are eligible and willing to take part they will formally consent to participation online and then be directed to the survey. Once we have filled the quota for each country (100 women; 90 using CHCs and 10 not) the link to recruitment will be removed. Participation will be incentivised by offering entry into a draw for a voucher to the value of 50 euro or equivalent local currency. The survey will consider the extent to which the findings from the interviews from WP 3 are transferrable to other European Union Member States. The survey will collect sociodemographic information including age, ethnicity, education and occupation and a measure (scores from 1-10) of women's perceived risk of VTE associated with taking CHCs. This method has been used successfully elsewhere to capture people's assessments of risk⁶. An important aspect of this survey is to explore what optimal communication from regulators would look like. This will be achieved through the presentation of a range of possible scenarios for improving communication, drawn from the qualitative work conducted in WP3. The internet survey will be conducted using REDCap, (Research Electronic Data Capture) a secure web application for building and managing online surveys and databases. This service enables data to be automatically captured and retained in a 'safe haven', ensuring rigorous research governance and data protection standards in relation to the survey data collected. This approach also eliminates the need for resources for data entry.

Analysis

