Surveys presented online generally get a reasonable response rate as people can answer questions at a time that is convenient to them, in privacy and with minimal effort, a key aspect being they don't need to speak to a researcher or receive or return an item by post. This also makes them cost-effective. Eligibility will be assessed via an initial filter page that will check potential participants are involved in advising about, and / or prescribing CHCs. If they are eligible they will formally consent to participation online and then be directed to the survey. Once we have filled the quota for each country the link will be removed. We will incentivise participation by offering entry into a draw for a voucher to the value of 50 euro or equivalent local currency, whenever allowed by local law. The survey will consider the extent to which the findings from the interviews from WP 4 are transferrable to other European Union Member States. The survey will be sent to health professionals via the European General Practice Research Network. An important aspect of this survey is to explore what optimal communication from regulators would look like. This will be achieved through the presentation of a range of possible scenarios for improving communication, drawn from the initial in-depth qualitative work. The survey will also collect sociodemographic information including age, ethnicity, occupation and a measure (scores from 1-10) of health professionals' views of perceived risk of VTE associated with taking CHCs. This method has been used successfully elsewhere to capture people's assessments of risk ⁷. The internet survey will be conducted using REDCap, (Research Electronic Data Capture) a secure web application for building and managing online surveys and

databases. This service enables data to be automatically captured and retained in a 'safe haven', ensuring rigorous research governance and data protection standards in relation to the survey data collected. This also eliminates the need for resources for data entry.

Analysis

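### Neither survey excludes people already interviewed, so professionals who were shown the EMA advice in WP4 could be counted in WP6 awareness; the effect is small and one filter question removes it

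*Protocol*

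**What the plan says.** All places are in the protocol, section 9.2, unless noted.

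- **Order.** The surveys are built from the findings of WP1 to WP4, so the interviews come first. The abstract's milestones put interviews and their analysis at month 12 and the survey at month 14.
- **Professionals, interview (WP4 Research Process).** "After providing their views we will show them the advice provided following the review by the EMA and ask them how familiar they are with" […]. On recruitment, WP4 Sample says only: "The place of recruitment will vary according to country".
- **Professionals, survey (WP6).** Recruitment is through primary care networks. The filter page checks involvement in advising on or prescribing CHC. The aim includes awareness of regulatory communication and testing suggestions raised in the WP3 and WP4 interviews.
- **Women, interview (WP3).** "We will recruit from universities and schools as they employ a range of people from cleaners and domestic staff to teachers and lecturers"; youth centres are added. On content: "Interviews will also explore women's awareness of regulators as a source of information about CHCs". Women are also asked how communication could be improved.
- **Women, survey (WP5).** "The survey will be distributed via local organisations such as schools, colleges and youth centres". The filter page checks age 16 to 49. Quotas are 90 CHC users and 10 non-users per country. Scenarios are drawn from WP3.
- **Purpose of the check.** WP6 states: "The survey will consider the extent to which the findings from the interviews from WP 4 are transferrable to other European Union Member States". WP5 says the same of WP3.

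Nothing in the protocol excludes or flags earlier interviewees in either survey.

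**The concern.** A professional who has just read the EMA advice in an interview, and then answers the survey, may report awareness that the study itself produced. The survey is meant to describe awareness as it exists in practice, so such answers push it upwards. A second route applies to both groups: someone who suggested an improvement in an interview may later be asked to rate a scenario built on that suggestion, which is not independent support for it.

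Either effect could arise only in the UK, Denmark and whichever of Slovakia or the Netherlands is chosen. Countries are to be compared descriptively, so any inflation would fall on some countries and not on others. It could not be removed afterwards from the survey items the protocol names (sociodemographic details, a risk score, responses to scenarios), because none of them records earlier participation.

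**Working it through.** **1. The plan's own totals.** WP3 and WP4 each say: "We will aim for 8 participants from each of the three target countries, with a lower limit of 6 and a higher limit of 10". 3 × 8 = 24 interviewees per group, as stated. 6 × 100 = 600 survey places per group, as stated. No power calculation is given, so there is none to reproduce.

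**2. Ceiling on overlap.** If every interviewee also answered the survey: 8/100 = 8% in each interview country, 24/600 = 4% overall, and 0 in the other three countries. One country could reach 10 (for example 10 + 8 + 6 = 24), but 10 in all three would be 30, above the stated cap of 24.

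**3. Effect on measured awareness.** Let k be interviewees in a country, f the share who re-enter, and p the awareness among all other respondents. The protocol gives neither f nor p, so both are assumptions shown over a range. Counting every re-entrant as aware (worst case):

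observed awareness = [k·f + (100 − k·f)·p] / 100, so the upward shift = (k·f/100) × (1 − p).

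With k = 8, in percentage points:

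| True awareness p | All re-enter (f = 1) | A quarter re-enter (f = 0.25) | 95% half-width, n = 100 |
|---|---|---|---|
| 10% | 0.08 × 0.90 = 7.2 | 0.02 × 0.90 = 1.8 | 5.9 |
| 30% | 0.08 × 0.70 = 5.6 | 0.02 × 0.70 = 1.4 | 9.0 |
| 50% | 0.08 × 0.50 = 4.0 | 0.02 × 0.50 = 1.0 | 9.8 |
| 90% | 0.08 × 0.10 = 0.8 | 0.02 × 0.10 = 0.2 | 5.9 |

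The half-width is 1.96 × √(p(1 − p)/100), given only for scale because the protocol plans no inference. At p = 10%, seven of the eight would have to re-enter (0.07 × 0.90 = 6.3) for the shift to exceed it. A single country with k = 10 and full re-entry gives 9.0 points at p = 10% and 5.0 at p = 50%.

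Pooled over six countries with k = 8 and full re-entry: 0.04 × 0.90 = 3.6 points at p = 10%, and 0.04 × 0.50 = 2.0 at p = 50%.

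**4. The small cell.** The WP5 non-user quota is 10 per country. Each non-user interviewee who re-enters is 1/10 = 10% of that cell. WP3 samples purposively on CHC use but gives no split, so the number at risk cannot be computed.

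**5. Which group has which ingredient.**

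| | Shown the advice in the interview | Interview and survey share a stated channel |
|---|---|---|
| Professionals (WP4, WP6) | Yes | No; WP4 channel left open |
| Women (WP3, WP5) | Not stated | Yes: schools, youth centres |

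Neither group is stated to have both. The rating of interview-derived suggestions does not need the first column and can arise in both groups.

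**The case against.** The strongest case against is that nothing in the protocol plans re-entry, and that exposure and shared channel are not stated together for either group. WP4 also covers gynaecologists, sexual health doctors and specialist nurses, some of whom may lie outside a general practice network, so full overlap is unlikely. Scenarios pool material from three countries, so one person's part in any of them is diluted. The surveys are descriptive convenience samples, and section 9.5 already says the data are unsuited to quantifying VTE-risk awareness across countries. The questionnaires are still to be developed, and a screening question could be added then. All of this stands as to size, and it makes the point minor. It does not close the gap: the protocol does state what each filter page checks, and those checks admit former interviewees. Section 9.5 also does not mention awareness of regulatory communication or ratings of suggestions.

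Stronger readings are tempting and are not supported:

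- A reader might infer that results in the interview countries are contaminated. The documents show only that they could be.
- A reader might take 8 to 10 points as the false gap between countries. That needs every interviewee to re-enter and nobody else to be aware, and 10 in every country breaks the cap of 24.
- A reader might assume that half the interviewed women are non-users and so place 4 of them in the cell of 10. The protocol gives no such split.
- A reader might treat interview versus non-interview countries as the defined test of transferability. No section defines it so. The protocol speaks of transfer to other Member States, and the three countries without interviews cannot be affected by this route.

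**Conclusion.** The point holds as a minor gap in survey eligibility. It matters most from WP4 to WP6, where the interview shows the advice and the survey then asks about awareness of regulatory communication. For women the exposure is limited to interview questions about regulators and improvements.

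The bias lies between zero and the ceilings worked out above. Those ceilings rest on assumed re-entry and baseline awareness, and on counting every re-entrant as aware. Within one country it would exceed ordinary sampling error only if awareness is low and nearly all interviewees re-enter. The WP5 non-user cell is the one place where a single person moves the figure by a visible amount. No test or power figure is affected, since none is planned.

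**What to change.** Add one question to the WP5 and WP6 filter pages asking whether the person has already been interviewed for this study, and make those who answer yes ineligible. Say so in both Sample sections, and tell interviewees at the end of the interview. If the team prefers not to turn people away, record the answer, report those respondents separately and leave them out of the country counts and the 90/10 quotas.

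With exclusion, and accurate answers to the question, the overlap and the shift are both zero. The cost is one question per survey and at most about 8 respondents per group per interview country to replace through the same recruitment routes.

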9.3. Data management

Identifiable data from interviews will be stored on secure servers in the country in which the data are collected. Anonymised transcripts will be provided to the UK for the purposes of analysis. The internet survey will be conducted using REDCap, (Research Electronic Data Capture) a secure web application for building and managing online surveys and databases. This service enables data to be automatically captured and retained in a 'safe haven', ensuring rigorous research governance and data protection standards in relation to the survey data collected.

9.4. Quality control

Final versions of all documents will be overseen by the lead researcher. The lead researcher will also closely supervise the research associate for each of the work packages; in particular the preparation of search terms for the literature and internet search and topic guides for the interviews with users and non-users of CHCs and health professionals, data collection plans and all the analysis. The lead researcher will also oversee the requirements for governance and ethics, with advice from local researchers.

There will be administrative support to ensure smooth running of the project and five steering group meetings, roughly spaced throughout the project. There will be patient and public involvement representatives asked to comment at each stage of the research (four time points) to ensure the analysis and subsequent findings make sense to people who would use them in the future.

The lead researcher is experienced in supervising as well as experienced in the proposed methodology, specific methods and topic of decision making. The wider consortium have previously worked together successfully on tenders for the EMA.

9.5. Limitations of the research methods

The project is a mixed methods study which will investigate awareness, perceptions and decisions about the use of regulatory communication concerned with the risks of venous thromboembolism among doctors, users and potential users of CHC. The data provided will be descriptive and explanatory. It will not be suited to statements of quantification across different European countries of awareness of the risks of VTE associated with use of CHC

and quantification of behaviours in relation to the prescription and use of CHC.

11. Protection of human subjects

Ethical approval will initially be obtained through the lead university (UCL), with associated linked approvals in Denmark, Germany, the Netherlands, Slovakia, and Spain.

12. Plans for disseminating and communicating study results

Summaries of the findings of the work will be offered to all participants. Abstracts will be submitted for conferences such as the European General Practice Research Network conference. The last deliverable is a paper for submission to an academic journal.

A project on women's choice of contraception is currently being conducted in the lead researcher's Department and the two projects will work together to share ideas and findings.

13. References

2. http://www.ema.europa.eu/ema/index.jsp?curl=pages/medicines/human/referrals/Combined_hormonal_contraceptives/human_referral_prac_000016.jsp&mid=WC0b01ac05805c516f
3. http://www.ema.europa.eu/ema/index.jsp?curl=pages/news_and_events/news/2013/11/news_detail_001969.jsp&mid=WC0b01ac058004d5c1
4. http://ec.europa.eu/eurostat/statistics-explained/index.php/Digital_economy_and_society_statistics_-_households_and_individuals
5. http://europa.eu/rapid/press-release_IP-03-550_en.htm?locale=en

Annex 1. List of stand-alone documents

Number	Document reference number	Date	Title
1	1.1	21/12/17	Gantt Chart

ENCePP Checklist for Study Protocols (Revision 3)

Adopted by the ENCePP Steering Group on 01/07/2016

The [European Network of Centres for Pharmacoepidemiology and Pharmacovigilance \(ENCePP\)](#) welcomes innovative designs and new methods of research. This Checklist has been developed by ENCePP to stimulate consideration of important principles when designing and writing a pharmacoepidemiological or pharmacovigilance study protocol. The Checklist is intended to promote the quality of such studies, not their uniformity. The user is also referred to the [ENCePP Guide on Methodological Standards in Pharmacoepidemiology](#), which reviews and gives direct electronic access to guidance for research in pharmacoepidemiology and pharmacovigilance.

For each question of the Checklist, the investigator should indicate whether or not it has been addressed in the study protocol. If the answer is "Yes", the section number of the protocol where this issue has been discussed should be specified. It is possible that some questions do not apply to a particular study (for example, in the case of an innovative study design). In this case, the answer 'N/A' (Not Applicable) can be checked and the "Comments" field included for each section should be used to explain why. The "Comments" field can also be used to elaborate on a "No" answer.

This Checklist should be included as an Annex by marketing authorisation holders when submitting the protocol of a non-interventional post-authorisation safety study (PASS) to a regulatory authority (see the [Guidance on the format and content of the protocol of non-interventional post-authorisation safety studies](#)). The Checklist is a supporting document and does not replace the format of the protocol for PASS as recommended in the Guidance and Module VIII of the Good pharmacovigilance practices (GVP).

Study title:

Study of regulatory communication and risk awareness following the Article 31 referral of Combined Hormonal Contraceptives in relation to thromboembolism

Study reference number:

EMA/602994/2015

Section 1: Milestones	Yes	No	N/A	Section Number
